Subject Replacement: Subjects who drop out will be replaced by screening the inpatient unit. Subjects that drop out will be followed for secondary outcomes collected via the EMR while they remain at TIRR.

4. TRIAL SCHEDULE:

Participants will be enrolled in the study upon consent within 48-72 hrs of admission to TIRR MHH or Craig Hospital, and participation will end on discharge from respective hospital. The trial will start upon IRB and respective hospital approval on July 1, 2021, and end on June 30, 2024.

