6. METHODS AND ASSESSMENTS

Intervention: Lower Vt group will be kept 8- 10 ml/kg pbw with PEEP, and in the high Vt group, the participant will receive a tidal volume of 14-16 ml/kg pbw with PEEP. The PEEP will be adjusted based on atelectasis on X-ray findings and patient tolerance within 5-10 cm H₂O range. These thresholds are used based on our cohort study²⁶ and survey data, which suggest the current median minimum to maximum Vt range used in rehabilitation hospital setting ranges from 8-16 ml/kg pbw. Tidal volumes will be increased per our institutional protocol at a rate of 50-100 ml per day until the target range is achieved. All participants at admission will be switched to Assist Control (AC) Mode or synchronized intermittent mandatory ventilation which is the current standard of practice in our free-standing acute inpatient rehabilitation unit. We will monitor peak and plateau pressures. All study participants will receive standard respiratory care, including secretion management using sub-glottic suction, mechanical insufflator-exsufflator, albuterol-ipratropium nebulization as-needed medications for thick secretions (e.g., N-acetylcysteine, guaifenesin).

Ventilator weaning Protocol is managed by board-certified SCI medicine rehabilitation physicians in our institution. Internal Medicine physicians are consulted on all our mechanically ventilated patients, and pulmonologists are available for consultation as needed. The ventilator

weaning protocol begins once the patient is determined to be medically stable by the attending physician and satisfies the following institutional criteria: lung auscultation with clear or relatively clear breath sounds, vital capacity >10-12 ml/kg pbw measured by Wright's spirometer via mouth or tracheostomy, chest X-ray clear or stable, arterial blood gas analysis on room air within normal limits, no active infection, hemoglobin >10 gm/deciliter and should be tolerating tracheostomy cuff deflation. The institutional weaning protocol consists of 12-19 days of progressive ventilator-free spontaneous breathing. The weaning schedule is adjusted sometimes due to respiratory complications, anxiety, and inability to tolerate protocol.

Control group: Both controls and people in mechanical ventilation groups will receive standard comprehensive inpatient rehabilitation services, including physical therapy, occupational therapy, speech, and respiratory therapy if needed.

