Outcomes: The **primary outcome is pneumonia episodes** with evidence of new or progressive and persistent infiltrate on chest radiograph plus 2 of the following abnormal white blood cell count, presence of fever or hyperthermia, purulent sputum, and deterioration in gas exchange.²¹ Any new pneumonia episodes which meet the above criteria and developed 48 hrs after achieving target Vt will be recorded. New pneumonia events can only be recorded after 14 days from the onset of the first event.

The **secondary outcomes** include feasibility outcomes. We will obtain the following data: a) **Recruitment rate:** the proportion of eligible people who provide consent (b) **Adherence rate:** the proportion of participants in each group who receive assigned intervention per protocol; (c) **Retention rate:** the proportion of participants in each group who complete all study procedures and d) **Missing data:** Percentage of missing data in each group. Based on only one RCT²⁵ performed in SCI comparing high vs. low Vt, we anticipate a total recruitment rate of 80% (i.e., that 80% of the eligible would consent for the study), and of those who are enrolled in the study, 80% adherence and retention rate will be observed. We anticipate <10% missing data.

Additional outcomes: This data will be collected from the time of admission to our rehabilitation hospital until discharge. a) b) **Other respiratory complications:** The following ventilator-associated events will be reported: transfer to acute care hospital due to respiratory complications, weaning failure, new pneumothorax, ARDS, pleural effusion, pulmonary embolism, atelectasis, and pulmonary edema, and c) total ventilator days, weaning days and hospital length of stay.

We will perform an analysis of MV-related lung injury biomarkers. Blood and tracheal aspirate samples will be collected at 3-time points; at baseline within 48 hrs of admission to AIR facility, 48- 72 hrs after achieving target Vt, and 3rd sample post- weaning or 2 weeks from target Vt. Samples will be processed and stored at -80 ° C until use in [name] laboratory located at the Medical School, University of Texas in Houston, TX. We will focus on IL-1, IL-6, IL-8, and TNF- α levels. For controls we will obtain blood samples within 48 hrs of admission and 2 weeks from baseline.

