Additional data: Additional data collection will include age, sex, weight, height, date of injury, date of admission to AIR, time since injury, mechanism of injury, American Spinal Injury Association (ASIA) impairment scale (AIS), vital capacity at admission, maximum vital capacity achieved during AIR stay, ventilator settings including Vt, peak and plateau pressure, hospital length of stay and discharge location. We will also collect information on any other ongoing or new infectious events other than pneumonia.

Randomization: Each subject will be randomized to either a tidal volume of 8-10 ml/kg pbw or 14-16 ml/kg pbw within 48 hrs of admission after obtaining consent. A 1:1 allocation ratio will be applied with permuted block size to maintain blindness and balance. Subjects will be stratified based on C1-C3 AIS A to ensure equal allocation of those with the most severe respiratory impairment and unlikely to wean from the vent. In our experience, C1-C3, AIS A was associated with lower vital capacity at admission. The study research assistant will randomize subjects in the redcap database, and he/she will not be involved in data analysis.

Blinding: The principal investigator (PI), statistician, outcome assessors, and participants will be blinded to tidal volume assignment.

Study Visits and Procedures:

Screening: Patients will be screened at the time of admission to TIRR Memorial Hermann. Respiratory therapist and SCI attendings will notify PI or research assistant (RA) regarding admits of an SCI patient dependent on mechanical ventilation or cervical SCI patients who are not dependent on MV (controls). PI or RA will discuss eligibility with respiratory therapists or attending physicians. PI may review discharge summary from acute care hospital or history and physical performed at TIRR admission to determine eligibility. If a person doesn't meet eligibility criteria, we will not save any identified data other than deidentified information on the reason for screening failure.

The screening will require information on age, past medical and surgical history, the duration of SCI, etiology of SCI, the dependence on a ventilator, neurological level and current medications.

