11. SAMPLE SIZE AND STATISTICAL METHODS

Determination of Sample Size:

The purpose of the proposed pilot trial is to test the feasibility of conducting a randomized control trial comparing high vs. low Vt MV. Given the complexity of this study and practice variation, it is essential to evaluate recruitment and study procedures. Our cohort study data suggest that approximately 19 patients per year will meet eligibility. Based on Fenton et al. study comparing high vs. low Vt MV in SCI, we anticipate a total recruitment rate of 80% (i.e., that 80% of the eligible would consent for the study), i.e., on average, we are expecting to enroll at least 10-12 participants with SCI who are on mechanical ventilation per year for mechanical ventilation group and total of 30 subjects for 3 years.

For the control group, we will recruit cervical SCI (neurological level C1-C5) who are not dependent on mechanical ventilation at admission to our acute inpatients rehabilitation facility. We plan to recruit a total of 15 subjects in 2 years. This is a pilot study based on feasibility of completing study within the above time frame this sample size was determined. We will have atleast 15 subjects in each group for the analysis.

Statistical and Analytical Plans:

Baseline data and unadjusted analysis of outcome variables will be presented as mean with standard deviation (SD) for a continuous variable with normal distribution otherwise as median with interquartile range (IQR). Categorical and ordinal data will be reported as totals and frequencies for baseline data and unadjusted analysis of outcome variables.

Aim 1: Respiratory outcomes: We will report relative risk with credible interval and posterior probability. We will use neutral prior, and for binary outcomes, this will be centered at RR of 1 with 95% credible interval of 0.3 to 3. Bayesian inference combines a prior or an estimated effect distribution based on previous studies and likelihood, which summarizes findings from the present study.³⁵ All Bayesian analyses will use similar models as the frequentist analyses. We will report risk ratios with 95% credible intervals and posterior probability of benefit or harm associated with the intervention.

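### Ventilator days and length of stay can be cut short by early transfer or death, and weaning days exist only in a subset formed after randomisation

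*Combined protocol and SAP*

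**What the plan says.** Section 6 (Outcomes) names pneumonia as primary and feasibility measures as secondary. A third tier of additional outcomes includes "total ventilator days, weaning days and hospital length of stay". The window is explicit: "This data will be collected from the time of admission to our rehabilitation hospital until discharge". Section 4 (Trial Schedule) agrees that "participation will end on discharge from respective hospital", and Section 6 (Study Visits and Procedures) takes outcome data from the medical record over the same stay.

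The three durations are not defined. Nothing says how to score a patient who dies, is transferred on the ventilator, returns after a transfer, goes home ventilated or never starts weaning. The plan does expect such patients. The same paragraph lists "transfer to acute care hospital due to respiratory complications, weaning failure, new pneumothorax, ARDS" among the reported events, and the stratification in Section 6 (Randomization) is meant to balance "those with the most severe respiratory impairment and unlikely to wean from the vent". Section 6 (Additional data) also collects "hospital length of stay and discharge location".

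Under Section 6 (Ventilator weaning Protocol), weaning starts only when the patient is judged medically stable and "satisfies the following institutional criteria". These include a vital capacity threshold, a clear or stable chest film and no active infection.

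Section 11 summarises continuous outcomes by mean and SD, or by median and IQR if they are not normally distributed. Aim 1 specifies relative risks, and the only prior given is for binary outcomes. There is no censoring or competing-event rule, and no effect measure for a duration.

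**The concern.** There are two separate problems.

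**Truncation.** Fewer ventilator days and a shorter stay would ordinarily be read as good. A patient who leaves early because of respiratory deterioration, or who dies early, also contributes few days. If one tidal volume causes more early exits, a plain mean or median can turn that harm into an apparent advantage.

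**Selection.** A patient who never meets the criteria to start weaning has no weaning period to measure. Meeting them happens after randomisation and can depend on the assigned tidal volume: absence of active infection is one criterion, and pneumonia is the primary outcome. Weaning days among starters therefore compare groups that randomisation no longer balances.

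The pilot is meant to show that its methods can work in a full-scale trial, and the effect of tidal volume on weaning is part of the controversy set out in Section 1. Measures left undefined here are likely to be carried forward.

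**Working it through.** The documents give no mean, SD, transfer rate or weaning rate for these outcomes, so there is no figure of theirs to reproduce. The only input taken from them is 15 patients per ventilated arm (Section 3). Every other value below is an assumption, chosen to show direction and range. Throughout, a transfer is taken to end the count.

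**1. Truncation, simplest case.** Suppose *k* of *n* patients leave on the ventilator at day *t*, and the rest average *m* ventilator days. Then

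mean = [(n − k)m + kt] / n

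and two arms with k₁ and k₀ such patients differ by (k₁ − k₀)(t − m)/n. With n = 15, m = 30 and t = 7:

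- three transfers: (12 × 30 + 3 × 7)/15 = 381/15 = 25.4 days
- one transfer: (14 × 30 + 1 × 7)/15 = 427/15 = 28.5 days
- difference: 2 × (7 − 30)/15 = −3.1 days, in favour of the arm with more transfers

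The sign is that of t − m. At t = 30 the difference is 0. At t = 40 it is 2 × 10/15 = +1.3 days.

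**2. Adding never-weaned patients.** Assume weaning at day 30, discharge at day 60 whether weaned or still ventilated, and transfer on the ventilator at day 10 without return.

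| Arm of 15 | Weaned / never weaned / transferred | Mean ventilator days | Mean stay (days) |
|---|---|---|---|
| Reference | 9 / 5 / 1 | (270 + 300 + 10)/15 = 38.7 | (840 + 10)/15 = 56.7 |
| More transfers | 7 / 4 / 4 | (210 + 240 + 40)/15 = 32.7 | (660 + 40)/15 = 46.7 |
| More never weaned | 6 / 8 / 1 | (180 + 480 + 10)/15 = 44.7 | (840 + 10)/15 = 56.7 |

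More transfers make an arm look better on both measures. More never-weaned patients make it look worse on ventilator days and leave the stay unchanged.

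**3. Timing of transfer.** In a simulation of 400,000 patients per scenario, transfers rise from 6.7% to 26.7%, 60% of the others wean at about day 30, and discharge is at about day 60.

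| Mean transfer day | 5 | 10 | 20 | 30 | 40 | 50 |
|---|---|---|---|---|---|---|
| Difference in ventilator days | −7.3 | −6.5 | −4.4 | −2.4 | −0.4 | +1.6 |
| Difference in stay (days) | −10.9 | −10.0 | −8.0 | −6.0 | −4.0 | −2.0 |

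The formula in step 1 agrees. Patients not transferred average 0.6 × 30 + 0.4 × 60 = 42 ventilator days, so the difference is about 0.20 × (t − 42); at t = 20 this is −4.4. For stay it is about 0.20 × (t − 60); at t = 20 this is −8.0.

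**4. Selection in weaning days.** Assume time to weaning is lognormal with median 28 days and log-SD 0.4. If the fastest 80% wean, the mean among weaners is 25.4 days. If only the fastest 60% wean, it is 22.4. The second arm looks 3.0 days better although nobody weaned faster and fewer weaned.

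**5. The same three arms on measures that include everyone.** Patients off the ventilator at discharge are 9/15 = 60%, 7/15 = 47% and 6/15 = 40%. Ventilator-free days to day 60, with zero for anyone who never comes off, are 9 × 30/15 = 18, 7 × 30/15 = 14 and 6 × 30/15 = 12. Both worse arms now score worse.

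**The case against.** The case for leaving this alone has substance. These are third-tier outcomes. No hypothesis in Section 2 concerns them, and no between-arm test of a duration is specified. Respiratory transfers and weaning failure are reported in the same paragraph, and discharge location is collected, so a careful reader would see an excess of transfers beside a low ventilator-day count. The documents do not say that an acute-care transfer counts as discharge. If counting resumes on return, truncation affects only those who do not come back. The apparent advantage in ventilator days also needs transfers to be early. All of this stands and limits the severity. It does not repair the measures: the reader would still have to correct the durations by eye, and the silence about transfer and return is part of the gap.

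A reader might infer two stronger claims that the documents do not support:

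- **That all three outcomes are counted only in patients who wean, so an arm with more never-weaned patients looks better throughout.** Nothing restricts ventilator days or length of stay in this way. Never-weaned patients accrue ventilator days up to discharge and raise the mean, as step 2 shows.
- **That patients who never start weaning escape being counted as weaning failures.** Weaning failure is undefined. It might include patients still ventilated at discharge, so the fault is a missing definition and not a demonstrated reversal.

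**Conclusion.** The concern holds in a limited form. Total ventilator days and length of stay stop at discharge and have no rule for transfer or death, so early exits on the ventilator can make the worse arm look better. With 15 per arm, two extra transfers on day 7 are worth 3.1 days under the stated assumptions. The size depends on timing, and for ventilator days the sign does too. It also depends on a transfer ending the count, which the plan leaves open. Separately, weaning days can be measured only in patients who start weaning, so they do not support a randomised comparison. Severity is low to moderate, because these are additional outcomes in a pilot with 30 randomised patients.

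**What to change.** Amend Section 6 (Outcomes) and Section 11 (Statistical and Analytical Plans) as follows.

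- **Weaning.** Compare the proportion of all randomised ventilated patients who are alive and off the ventilator at final rehabilitation discharge. Count as not weaned those who never start weaning, those who die, and those transferred on the ventilator who do not return. This is binary, so the relative-risk model and prior already in Section 11 apply.
- **Duration.** Use ventilator-free days from randomisation to a pre-stated fixed day, in all randomised ventilated patients. Score zero for death or for never coming off the ventilator. Carry status at discharge forward to the fixed day. Resume counting for patients who return after a transfer.
- **Raw counts.** Keep ventilator days, weaning days and length of stay as descriptive only, tabulated by arm beside transfers and discharge location. State the number of patients contributing to weaning days.
- **Definitions.** State the start and stop of each duration, whether a transfer ends it, and what weaning failure means.

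The cost is mainly wording. The record must hold dates on and off the ventilator and dates of transfer and return, most of which total ventilator days already needs. The fixed day and the carry-forward rule are conventions. Day 60 above is only illustrative, and the day should be chosen before data are seen by arm. Since the protocol expects some patients not to wean, many scores may be zero. That makes ventilator-free days coarse with 15 per arm, and is a reason to let the proportion off the ventilator carry the comparison.

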7. TRIAL MATERIALS

The intervention proposed in this study doesn't need new equipment. Study intervention involves adjusting their current ventilator settings. Clinical outcome measures will be collected from electronic medical records in respective hospitals.

Inflammatory markers will be analyzed from blood and tracheal samples of participants. ELISA assays to assess markers of inflammation. A Millipore Multiplex MAP® 37-plex human cytokine panel (EMD Millipore, Billerica, MA, USA) will be used. Laboratory supply will include pipettes, tubes, reagents, chemicals, and gauze. The majority of the equipment required is provided by the institution and/or is part of the standard of care at TIRR Memorial Hermann or available at UTHealth for research use. E.g., Office space, computers, and access to MS office software for creating data collection report forms. RA or PI will transport samples after collection for storage and analysis to [name] lab.

Storage of blood and tracheal specimens: Samples will be processed and stored at -80°C until use in [name] laboratory located at the Medical School, University of Texas in Houston, TX and Craig Hospital Biorepository laboratory located at Craig Hospital, Englewood, CO.

8. TREATMENT

The current clinical practice guidelines recommend a higher tidal volume starting at 15 ml.kg predicted body weight (pbw) and up to 25 ml/kg pbw. These guidelines were written based on a small retrospective study and biological plausibility. People with SCI suffer hypoventilation due to paralysis of the muscle of inspiration. However, current data in people with and without ARDs suggests that lower tidal volume lowers the risk of morbidity and mortality and improves respiratory outcomes. Cohort study performed at TIRR also suggests that lower tidal volumes may lower the risk of pneumonia.

Our cohort study and a recent survey of physicians managing mechanical ventilators for people with SCI suggest practice variation in ventilator settings used for people with SCI.

Data from our center and international survey:

Variation in ventilator settings used for patients with acute SCI in acute care hospital at the time of discharge to a rehabilitation facility (Unpublished data): We collected data on 91 patients who required mechanical ventilation at the time of admission to acute inpatient rehabilitation (AIR) facility from 2015-2019. We noted variation (Figure 1.) in ventilator modes and settings used at acute care hospitals at the time of discharge. Median (interquartile range) tidal volumes were 7.5 (6.7-8.5) ml/kg pbw on admission to AIR facility or at the time of transfer from acute care hospital. 84% of patients were receiving PEEP on admission. After admission to the AIR facility, all patients were weaned off PEEP within the next 1-2 days and switched to assist control mode. Patients' tidal volumes were gradually increased to prevent atelectasis per SCI clinical practice guidelines.⁴ As a result, the median (IQR) tidal volumes received in rehabilitation hospital were 14 (13-16) ml/kg pbw. Our data suggest that ventilator settings used in acute care hospital and rehabilitation vary.

[figure not shown]

Figure 1: Ventilator modes at the time of discharge from acute care hospital

Abbreviations: Assist control; **SIMV:** Synchronized intermittent mandatory ventilation; **PS:** pressure support; **CPAP:** Continuous positive airway

Variation in ventilator settings used in acute care hospital and rehabilitation facilities across the globe for patients with acute SCI (manuscript under review): We conducted an international online survey of providers from acute care and rehabilitation hospitals to identify practice variations in the management and weaning of mechanical ventilation in patients with acute SCI. We received 137 responses from 33 countries. The highest Vt [median (interquartile range)] reported by acute care was 10 (8-10) ml/kg pbw compared to 13 (10-15) ml/kg pbw ($p=0.001$) in the rehabilitation setting. Application of PEEP and keeping the tracheostomy cuff inflated are commonly reported practices in acute care, whereas there is inconsistency with these practices in the rehabilitation setting. Regarding factors to initiate weaning, physicians in acute care mostly relied on arterial blood gas (70%) findings, whereas in the rehabilitation setting, physicians relied on vital capacity (73%). We found important differences in practices between "acute care and rehabilitation setting" and "within a rehabilitation setting."

The proposed ventilator settings are within the currently used ventilator settings across the globe and in our institution. Our proposed study compares tidal volume ranges of 8-10 ml/kg pbw and 14-16 ml/kg pbw. After reviewing our institute's data, current practice (survey results), and current literature in the non-SCI population, these settings were proposed. Tidal volumes are delivered via a mechanical ventilator used routinely in clinical practice.

Concomitant therapy: Patients in MV group will undergo ventilator weaning and respiratory care for secretion management per institution standard protocol. We will collect information on all medications taken by the participant during the study period. Controls will receive medical and rehabilitation therapies per current institution standard protocol.

Blinding: A panel of SCI attendings and a pulmonologist will determine the primary outcome. Deidentified data on respiratory events will be discussed with the team to determine if that event meets our diagnostic criteria for pneumonia and other ventilator-associated events. Data will be collected and presented by RA trained by PI. Inflammatory markers data from MV group and controls will be analysed by a blinded assessor.

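### The promised blinding of the pneumonia assessors is not secured by the adjudication procedure the protocol describes

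*Combined protocol and SAP*

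**What the plan says.** **The promise.** The Blinding paragraph of Section 6 lists the principal investigator and statistician, then adds "outcome assessors, and participants will be blinded to tidal volume assignment". Section 5 says the same. The research assistant is on neither list.

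**The panel.** Section 8 (Blinding): "A panel of SCI attendings and a pulmonologist will determine the primary outcome". Its material is described as follows: "Deidentified data on respiratory events will be discussed with the team to determine if that event meets our diagnostic criteria for pneumonia". The same discussion covers the remaining respiratory complications. On who supplies the material, the paragraph says: "Data will be collected and presented by RA trained by PI".

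**Allocation.** Section 6 (Randomization): "The study research assistant will randomize subjects in the redcap database, and he/she will not be involved in data analysis".

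**Who treats.** Section 6 (Methods): "Ventilator weaning Protocol is managed by board-certified SCI medicine rehabilitation physicians in our institution". Under Screening, Section 6 also has SCI attendings telling the study team about ventilated admissions.

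**The outcome.** Section 6 (Outcomes) requires a new, or progressive and persistent, infiltrate plus two of four signs, which include purulent sputum and worsening gas exchange. It counts episodes that "developed 48 hrs after achieving target Vt will be recorded". Tidal volume and peak and plateau pressures are among the data collected (Additional data).

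**On the other side.** Section 12 says the principal investigator and collaborators have no inpatient service.

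**The concern.** A promise of blinding is only as good as the procedure behind it. Here the only safeguard described for the panel is de-identification, which hides who the patient is but not which tidal volume was set. Three routes to the arm are left open.

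1. A panel member may be treating the patient, or may recognise the case among the 30 ventilated patients planned at two hospitals over three years.
2. The packet may contain ventilator settings, pressures or titration dates.
3. The person who collects and presents events may know the allocation and may influence which events are put forward and how.

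Parts of the pneumonia definition call for judgement: whether an infiltrate is progressive, whether sputum is purulent, whether gas exchange has worsened. With 15 patients per arm and a criterion of more than 70% posterior probability (Hypothesis 1), a few borderline calls could decide whether the hypothesis is reported as met. Section 1 says the pilot is to show that its methods can work at larger scale, so the gap would also carry into the larger trial.

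**Working it through.** The plan states no figure on this point, so there is none to reproduce. There are three checks.

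**1. What the text requires and what it leaves open**

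| Question | Stated | Not stated |
|---|---|---|
| Are assessors blinded to tidal volume? | Yes (Sections 5 and 6) | How this is achieved |
| Who are they? | SCI attendings and a pulmonologist (Section 8) | That they are not treating the patient |
| What do they see? | De-identified event data (Section 8) | That tidal volume, pressures and titration dates are removed |
| Who presents? | A research assistant (Section 8) | That this person is not the one who randomises, or that every candidate event is forwarded |
| What is the randomising assistant barred from? | Data analysis (Section 6) | Event collection and presentation |

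In the same Section 8 paragraph the biomarker assessor is called blinded. The pneumonia panel is not.

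**2. Would the target date reveal the arm, if the panel saw it?**

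Inputs: admission tidal volume, median 7.5 ml/kg pbw, IQR 6.7 to 8.5 (Section 8); steps of 50 to 100 ml per day (Section 6); lower edges of the targets, 8 and 14 ml/kg pbw (Section 6). Predicted body weight is not given; 50 to 80 kg is assumed.

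Days = (target − admission value) × weight ÷ daily step, rounded up.

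- Low arm from the median: (8 − 7.5) × 50 = 25 ml to (8 − 7.5) × 80 = 40 ml, so 1 day.
- High arm from the median: (14 − 7.5) × 50 = 325 ml to (14 − 7.5) × 80 = 520 ml, so 4 to 6 days at 100 ml per day and 7 to 11 days at 50 ml per day.
- Across the admission IQR: 0 to 3 days (low) and 3 to 12 days (high).

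The ranges barely touch, so the date would usually give the arm away. Two conditions apply. No text sends this date to the panel. And the Section 6 schedule puts titration on Days 1 to 4 for both arms, which would narrow the difference if it is kept.

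**3. How many shifted calls matter?**

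Inputs: prior on the relative risk centred at 1 with 95% interval 0.3 to 3 (Section 11); 15 per arm (Section 3); criterion above 70% (Section 2). The pneumonia rate is not stated, so a range of counts is assumed.

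Prior on log RR: mean 0, SD = ln(3)/1.96 = 0.5605, precision 1/0.5605² = 3.183. Likelihood (normal approximation), with a low-arm and b high-arm events: log RR = ln(a/b), variance = 1/a − 1/15 + 1/b − 1/15.

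For 4 vs 6: log RR = −0.4055; variance = 0.2833; precision 3.529. Posterior mean = −0.4055 × 3.529/(3.529 + 3.183) = −0.2132; SD = 1/√6.712 = 0.386. P(RR < 1) = Φ(0.2132/0.386) = 0.710.

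| Equal counts | After one fewer low-arm and one more high-arm event | P(RR < 1) |
|---|---|---|
| 3 vs 3 | 2 vs 4 | 0.696 |
| 4 vs 4 | 3 vs 5 | 0.704 |
| 5 vs 5 | 4 vs 6 | 0.710 |
| 6 vs 6 | 5 vs 7 | 0.715 |
| 7 vs 7 | 6 vs 8 | 0.722 |
| 8 vs 8 | 7 vs 9 | 0.731 |

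Equal counts give 0.500. A single shifted call gives about 0.61 (4 vs 5: 0.610; 5 vs 6: 0.613). The stated prior interval is not quite symmetric on the log scale. Taking the SD from its lower limit, ln(1/0.3)/1.96 = 0.614, moves 2 vs 4 to 0.707, so that row sits on the boundary.

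**The case against.** The strongest reply is that the protocol does bar the panel from knowing the arm: Sections 5 and 6 say so without qualification, and only the operating detail is missing. That is right, and it limits the point to procedure.

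A reader might go further and infer that the panel members are the clinicians ventilating these patients, so that the blinding has already failed. The documents do not support that. They show a shared specialty and job title, not shared persons. Section 12 points the other way for the principal investigator and collaborators, although it does not say whether panel members count as collaborators. A reader might likewise infer that one assistant both randomises and presents. One role need not be one person, and a presenter who knows the arm does not by itself unblind a panel. Nor is it shown that the panel sees the target date: Section 8 asks it to apply the diagnostic criteria, and the 48-hour rule could be applied by someone else.

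The illustration is also fair to challenge. It needs two errors in opposite directions, and at 2 vs 4 it falls just short under the main prior. Much of the fragility comes from the 70% criterion and the sample size. With perfect adjudication and an assumed true risk of one third in both arms, summing the binomial probabilities of all tables above 0.70 (zero cells counted as not crossing) gives about 26%. That is a separate matter, but it means adjudication is not the only way to cross by accident.

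Finally, the direction of bias is not settled. Hypothesis 1 favours low tidal volume, but Section 8 reports that the centre's own practice had been to raise volumes to a median of 14 ml/kg pbw, so attendings' leanings could run either way. Section 11 gives feasibility as the pilot's purpose, yet Section 6 makes pneumonia the primary outcome, so its masking still matters.

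**Conclusion.** The point holds as a gap in procedure: assessor blinding is promised in Sections 5 and 6 and is not secured by what Section 8 describes. Followed as written, the plan allows an assistant who knows the allocation to select and present events, on a partly judgement-based primary outcome, to a panel that may include treating physicians and may see arm-revealing data. None of this is shown to happen; it is not excluded.

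On size, about two differential calls could carry equal counts across the 70% criterion, and one could not. This rests on a normal approximation, 15 evaluable patients per arm and assumed event counts, and says nothing about how likely such calls are. The inference from the target date is conditional on the panel seeing it and on the assumed body weights. The gap should be closed, because the remedy is cheap and the outcome is primary.

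**What to change.** Amend the Blinding paragraph of Section 8, keeping the existing panel.

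- **Packet.** Remove tidal volume, peak and plateau pressures, and titration and target dates. Keep only the gas-exchange information the criterion needs, in an arm-neutral form. Have someone outside the panel apply the 48-hour rule.
- **Panel.** Members do not adjudicate patients they treat; use members from the other hospital where possible. If members are already non-treating, one sentence saying so is enough.
- **Presenter.** Forward every event that meets a pre-set objective trigger, without selection. Where possible the presenter is existing staff without access to allocation.

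The cost is protocol wording and packet redaction. Scheduling becomes slightly harder because of recusal, and the panel has less ventilator context when judging gas exchange. No treatment rule changes.
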